2.4. Definition of Seizure

If the patient has a seizure they should contact their treating team. The patient should be reviewed by a neurologist to confirm whether a seizure has taken place.

For study purposes, confirmed seizures will include any of the following:

- 1. Simple partial seizures:
 - a) with motor symptoms: focal motor movements, versive/postural movements
 - b) with sensory symptoms: olfactory sensations
 - c) with autonomic signs
 - d) with psychic symptoms (e.g. déjà vu, jamais vu)
- 2. Complex partial seizures
 - a) with impairment of consciousness only
 - b) with impairment of consciousness plus automatisms (lip smacking, fumbling, etc.)
- 3. Partial seizures with secondarily generalized seizures
 - a) Unconsciousness with generalised clonic movements
 - b) Unconsciousness with generalised tonic spasm, without clonic movements
 - c) Unconsciousness or staring with one of the following preceding symptoms perceived by the patient:
 - A rising feeling from the abdomen to the throat
 - Smelling of odd scents
 - Stiffening or convulsions in the face or limb(s)
 - Turning the head to one side.

Excluded attacks are those deemed by the treating physician not to be epileptic seizures.

2.5. Patient Reported Outcomes for Quality of Life

This study seeks to establish whether the use of levetiracetam reduces the occurrence of seizures. However, given the potential side effects and symptoms associated with both seizures and the use of AEDs, it will be important to determine whether any determined benefit is associated with improvements in symptoms.

There have been efforts in neuro-oncology to evaluate secondary endpoints using validated instruments as additional indicators of benefit.

The Patient Reported Outcomes will form part of the initial secondary outcome analysis to determine whether there is a difference in Quality of Life (QoL) between the treatment groups. The data will be collected in line with clinic visits at pre surgery (baseline), 3 months, 6 months, 9 months and 1 year.

Patient Related Outcome Objectives

- To evaluate longitudinal changes in symptom measures and determine the impact of the use of AEDs on these parameters.
- To measure symptom burden over the course of the study period (one year) to evaluate differences between patients' individual symptom severity, overall mean symptom severity, and difference in scores on the interference items between those not taking prophylactic medication versus those on levetiracetam.
- To describe the variability of symptom severity longitudinally over the follow-up period.

Patient Related Outcome Instruments

LAEP (Liverpool Adverse Events Profile)

This is used as a systematic measure of adverse effects from anti-epileptic drugs (AED). Patients will complete LAEP pre surgery (baseline) and 3 monthly to coincide with clinic visits. Patients may elect to complete paper questionnaires or receive them via an email link for online completion. The patients carer or research assistant (if attending clinic or completing via telephone) may read the questions to the patient or assist with marking the severity number or score as described by the patient. The patient's carer may complete the questionnaires as a patient-preference proxy if the patient's deficits preclude self-report. These reports will be used for descriptive purposes only.

EQ-5D-5L

This is a standardised instrument for use as a measure of health outcome developed by the EuroQoL Group that facilitates the calculation of Quality Adjusted Life Years. It should take approximately 5 minutes to complete. Patients will complete EQ-5D-5L at pre surgery (baseline) and 3 monthly to coincide with clinic visits. Carers will also be asked to complete the Proxy version 1 of the EQ-5D-5L Questionnaire; this asks the carer how they would rate the patients health. The EQ-5D-5L Telephone version will also be collected through a telephone interview with a research nurse when the participant experiences their first episode of seizure like symptoms during the trial period. The patient will continue to complete the questionnaires at the time of clinical and seizure evaluation as long as the patient remains on the study, unless clinical deterioration makes self-reporting not possible before that time. The time when patients are unable to complete the self-report questionnaires will be used as part of the study analysis.

For EQ-5D-5L there will also be an online, face to Face and a telephone version where the carer or Research Nurse can complete on behalf of the patient. In addition, if the patient is unable to communicate their answers, a Proxy 2 version will be available – this is how the carer thinks the patient would rate his/her own health. The Carer will also have the option to complete the Proxy 1 EQ5D-5L online.

Patient Health Questionnaire-9 (PHQ-9)

PHQ9 is a screening tool for depressive symptoms. This instrument is included in recognition of FDA and MHRA advice that AEDs, including levetiracetam, can cause an increased risk of suicidal ideation - although the absolute risk is very low (in licensing studies, prevalence of suicidality on Levetiracetam=0.44%). Prior to randomisation and at the three monthly visits,

patients will complete the PHQ-9 rating scale for depressive symptoms, this will be available on paper, via telephone or an online link sent via email. This widely-used, nine-item rating scale records the patient's report of the frequency of depressive symptoms occurring over the past fortnight. The range of possible PHQ-9 scores is from 0 (no depression) to 27 (highest possible score). The result will be used in ways to promote patient safety on-study.

First, patients scoring \geq 20 will be categorised as having 'severe' depressive symptoms. They will be excluded from the study at entry, or during study, and the local clinical team informed. From pilot data in similar populations our starting assumption is that roughly 4% of patients will fall into this category.

Second, all patients will be excluded from the study should they answer >0 to PHQ9 Item 9.

Third, patients who score 15-19 on the PHQ-9 will be notified to their usual clinical team, as having 'moderately severe' depressive symptoms, for them to be aware and assess as they feel appropriate.

The Liverpool Impact of Epilepsy Scale (LIES) and the Liverpool Seizure Severity Score (LSSS)

Patients will be provided with a diary to track any possible seizure events. The Liverpool Impact of Epilepsy Scale (LIES) and the Liverpool Seizure Severity Score (LSSS) will be completed after first seizure and then again one year after randomisation: this is used to assess the impact of epilepsy on a number of different aspects of daily life.

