3. TRIAL DESIGN

3.1. General Design

This is a two arm, multicentre phase III randomised trial of prophylactic anti-epileptic drug (Levetiracetam) versus no anti-epileptic drug (AED) (comparator) in patients with suspected cerebral glioma.

Randomly assigned - 1:1 basis

This will not be a blinded study and will not have placebo control and as such will be a "real world" study of prophylactic AED vs. no AED. The reasons for the lack of placebo arm include; real world nature of the study, patient involvement feedback on the design with specific reference to value of a placebo arm; over-encapsulation as levetiracetam capsules are large; and cost of the study.

804 patients will be recruited and randomised into one of two arms:

- **Group 1**: Levetiracetam 500mg twice daily for 2 weeks, then increasing to 750mg twice daily thereafter for 1 year. Patients should have a minimum of 2 doses of 500mg prior to surgery. (In those with moderate chronic kidney disease stage 3 estimated Glomerular Filtration Rate (eGFR 30-59 mL/min/1.73 m²) a starting dose of 250mg twice a day for 2 weeks, then increasing to 500mg twice a day thereafter).
- **Group 2**: no AED treatment (standard care)

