3.4. Randomisation

After ensuring that the patients meet **all** eligibility criteria and has consented to participate in the study, sites will randomise the patient following the instructions described in the 'SPRING work instructions for sites.

Once a patient has been randomised, a patient study number will be issued and this should be used in all correspondence.

Informed Consent/Authorisation

All Patients that are eligible to receive therapy and randomised to AED arm must undergo an Electrocardiogram (ECG) and pregnancy test (if female and of child bearing age) prior to starting trial medication. AED arm patients must initiate treatment prior to surgery and have taken a minimum of two doses of 500mg Levetiracetam (two doses of 250mg in CKD3 patients) prior to surgery. See Patient Pathway (Page 7).

Prior to protocol enrolment and initiation of treatment, subjects must sign and date an approved consent form.

Eligibility Exceptions

Eligibility exceptions will not be granted.

Withdrawal of Subjects

Patients *discontinue* from the study drug for reasons such as safety or non-compliance. These patients will continue to be followed up for efficacy and safety as per protocol, unless they are lost to follow up or deceased. Patients may *withdraw* from the study at any point and they do not have to give a reason. However, we will ask the patient's permission to continue to collect information on their progress that is routinely recorded in their medical records. This is so that the overall quality of the study is not impaired. The patient can say no at this point and then no further data collection will take place, and will be censored at the point of withdrawal. This should be indicated on the case report form (CRF) as per completion guidelines.

Patients who consent to the trial but do not undergo planned surgery will be withdrawn from the trial. For any patient that did not undergo planned surgery, a further patient would be enrolled to the trial to maintain the target number of patients for analysis.

Please note that should it be medically required, participants in either study arm will be removed from the study and treated with appropriate medication according to standard care.

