Patients on the levetiracetam arm who have prolonged QT as detected by pre-surgical ECG and QT interval ≥500milliseconds will not start taking levetiracetam. These patients will **not** be withdrawn but, a further patient would be enrolled to the trial to maintain the target number of patients for analysis

Criteria for Removal from Study Drug

- Patient wishes to come off levetiracetam.
- Unacceptable toxicity (as defined in Section 4.4)
- Seizure (as defined in Section 2.4). Where patients taking levetiracetam develop a seizure, they will stop taking the study drug and move to a prescribed treatment dose from the treating clinician, this will most likely be maybe a higher dose of levetiracetam. The patient may voluntarily withdraw from treatment at any time for any reason.
- Neurological progression e.g. development of dysphasia

- Pregnancy (all female patients of child bearing age on the levetiracetam arm will complete pregnancy testing prior to starting trial medication and will complete a pregnancy test at any time the patient confirms there is a possibility of pregnancy)
- Severe depression as defined by a PHQ-9 score of ≥20
- Suicidal ideation on interview.
- Prolonged QT (QT interval 2500milliseconds) as detected by ECG prior to surgery

NOTE: Unless the treating clinician advises an immediate stop of Levetiracetam for safety reasons, patients will be issued with a taper pack to minimise side effects.

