4.5. Concomitant Therapy

Anti-tumour Treatment:

• Standard and experimental anti-tumour therapies are permitted.

Supportive Care:

- Dexamethasone should be used in the smallest dose to control symptoms of cerebral oedema and mass effect, and discontinued if possible.
- Febrile neutropenia may be managed according to the local institution's Infectious Disease guidelines. Measures may include appropriate laboratory testing, including blood and urine cultures and the institution of broad-spectrum antibiotics. If a source for the fever is not identified or the fever resolves when the neutrophil count recovers, antibiotics may be discontinued and the patient observed.
- The use of anti-emetics will be left to the investigators' discretion.
- Methotrexate use is an exclusion criteria and as such methotrexate should not be prescribed to patients enrolled in this trial. Where it is considered necessary to prescribe methotrexate patients should be removed from the trial.
- Therapies considered necessary for the wellbeing of the patient may be given at the discretion of the investigator. Other concomitant medications should be avoided except

for analgesics, chronic treatments for concomitant medical conditions, or agents required for life-threatening medical problems. All concomitant medications must be recorded.

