7.3 Analysis Plan

The primary analysis will be performed on the intention-to treat population. A full statistical analysis plan will be developed prior to any analysis being performed.

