7.3.1 Primary Efficacy Analysis

The primary analysis will be performed on the intention to treat population. A full statistical analysis plan will be developed prior to any analysis being performed.

One year occurrence of seizure

The occurrence of seizures within one year of randomisation will be compared between the study arms. The odds ratio, associated 95% confidence intervals and 2-sided p-values associated with the comparison of the arm from a logistic regression model fitted to the

presence of a seizure within one year of randomisation will be given. The estimated absolute difference in seizure rate will be reported together with associated 95% confidence interval.

This is the primary comparison.

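### Randomised patients are told to leave the study for events after randomisation, which conflicts with the stated intention-to-treat analysis and with the protocol's own rule that patients who stop drug stay in follow-up

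*Protocol*

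**What the plan says.** **Analysis.** Section 7.3 states: "The primary analysis will be performed on the intention-to treat population". Section 7.3.1 repeats this and sets the outcome as seizure within one year of randomisation. On blinding, Section 3.1 says: "This will not be a blinded study and will not have placebo control".

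**Rules under which a randomised patient leaves the study**
- Section 2.5, PHQ-9 score of 20 or more: "They will be excluded from the study at entry, or during study, and the local clinical team informed". The same section excludes any patient with a non-zero answer to item 9, with no timing given.
- Section 3.4, surgery cancelled: "Patients who consent to the trial but do not undergo planned surgery will be withdrawn from the trial".
- Section 3.4, medical need: "should it be medically required, participants in either study arm will be removed from the study and treated with appropriate medication". The need is not defined.
- Section 4.5: "Where it is considered necessary to prescribe methotrexate patients should be removed from the trial".

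**Replacement.** For non-operated patients, Section 3.4 adds that "a further patient would be enrolled to the trial to maintain the target number of patients for analysis". The same clause follows the rule for levetiracetam patients with a prolonged QT interval, but those patients are expressly not withdrawn.

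**Rules that point the other way.** Section 3.4 also lists a PHQ-9 score of 20 or more under removal from study drug. It says that patients who discontinue drug continue to be followed for efficacy and safety.

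**The concern.** An intention-to-treat analysis needs the outcome of every randomised patient, whatever happened after allocation. Sections 2.5, 3.4 and 4.5 tell sites to end participation for events that occur after allocation, in a trial where the arm is known. Two of the triggers deserve particular care.

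- PHQ-9 can be affected by treatment. Section 2.5 includes it because anti-epileptic drugs can raise the risk of suicidal ideation, and Section 1.5 lists low mood and behaviour change among the effects of levetiracetam.
- Medical need is judged by staff who know the arm.

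Two things are at stake. The primary odds ratio could be distorted if leaving differs by arm and is related to seizure risk. And PHQ-9 is itself compared between arms in Section 7.3.2, so a rule that removes patients at the top of the scale cuts short the outcome being compared.

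These are instructions on conduct. A later analysis plan can define the analysis set, but it cannot recover outcomes that sites were told to stop collecting.

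**Working it through.** **1. The same patient under two sections.** Take a levetiracetam patient who scores 20 at month 3.
- Under Section 2.5 the patient is excluded from the study. Questionnaires continue only while the patient remains on the study (2.5).
- Under Section 3.4 the patient stops drug and is followed for efficacy and safety.

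A site cannot do both. The offer in 3.4 to go on collecting routine-record data is written for patients who choose to withdraw. It does not clearly cover those whom the protocol removes.

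**2. Non-operated patients.** The one-year clock starts at randomisation (7.3.1), and randomisation may follow a telephone consent before the pre-surgical visit (10.2). A seizure between randomisation and a cancelled operation is therefore a primary outcome event. Withdrawing the patient, and enrolling another to hold the number for analysis, implies that this event is not analysed.

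**3. The plan's own sample size (7.1).** Inputs: 20% v 10%, two-sided 5%, power 90%, 1:1.
- n per arm = [1.96 × √(2 × 0.15 × 0.85) + 1.2816 × √(0.16 + 0.09)]² / 0.10² = 265.9, so 266 per arm and 532 in total. Power at 266 is 0.900.
- Events: 266 × (0.20 + 0.10) = 79.8.
- Inflation: 532 / (0.752 × 0.88) = 803.9, so 804.

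The plan's figures reproduce. The sample size arithmetic is not at fault here.

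**4. Equal removal, no bias.** Section 2.5 expects roughly 4% to score 20 or more, without saying whether at entry, on study or both. Taken wholly as on study, this is 0.04 × 804 = 32 patients, about 16 per arm.
- Evaluable per arm: 402 × 0.752 × 0.88 × 0.96 = 255.4. Power is 0.888.
- With no true effect, equal removal leaves the odds ratio at 1.00 and type I error at 5%.

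Section 2.5 gives no rate for item 9.

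**5. Unequal removal (assumed inputs).** The risk among those kept is (p − f·r)/(1 − f), with f the fraction removed and r their seizure risk. This supposes that all seizures of removed patients are lost. True risk is 20% in both arms, with 266 per arm before removal.

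| Removed, control v levetiracetam | Risk in the removed | Null OR becomes | Type I error |
|---|---|---|---|
| 4% v 4% | any | 1.00 | 5% |
| 2% v 6% | twice | 0.945 | 5.7% |
| 2% v 6% | three times | 0.890 | 8.0% |
| 2% v 10% | twice | 0.887 | 8.2% |
| 2% v 10% | three times | 0.776 | 18.9% |
| 2% v 6% or 2% v 10% | same | 1.00 | 5% |

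**6. The sign is not fixed either.** On-study PHQ-9 is three-monthly (4.3), and Section 7.1 puts seizures in the first post-operative week at up to 5%, so some removed patients would already have a recorded seizure. Suppose 10% of one arm is removed at 30% risk, and half of their seizures come first and are kept. Then events are 0.17 + 0.015 = 0.185, the denominator is 0.90 + 0.015 = 0.915, and the observed risk is 20.2%, above the true 20%. At 40% risk it is 0.18/0.92 = 19.6%.

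**The case against.** The case for treating this as drafting only has real weight.

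- A reader might infer that patients are removed for reasons that depend on arm or on the outcome. The text does not say so. Every rule for leaving the study is worded for both arms or without regard to arm. The arm-specific checks, for QT interval and pregnancy, stop or prevent study drug only. Seizure is a reason to stop study drug, not to leave the study.
- A reader might infer that QT patients are swapped out. They are kept, and the only fault there is the closing words of the replacement clause. Enrolling an extra patient does no harm if the first one is analysed.
- A reader might infer a definite false benefit. Removing 5–10% of the levetiracetam arm alone, at 30–40% seizure risk and with all their seizures lost, gives an observed 19.5% down to 17.8% against a true 20%. The document supports neither the one-arm removal nor the complete loss.
- Leaving follow-up produces a missing outcome. It does not by itself take a patient out of the intention-to-treat set, and the unseen analysis plan may deal with that.
- The primary objective concerns patients undergoing surgery, and nothing suggests that cancelled surgery or methotrexate differs by arm.

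All of this stands as a limit on the claim of bias. It does not resolve the contradiction between 2.5 and 3.4, the implied omission of non-operated patients from an analysis called intention to treat, or the loss of later PHQ-9 scores.

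**Conclusion.** The point holds as an internal contradiction with a possible, unquantified effect on the primary result. The protocol promises an intention-to-treat analysis over one year from randomisation and then directs that some randomised patients leave the study. For PHQ-9 it also gives two incompatible instructions.

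- **Primary outcome.** The rules can bias the comparison, but only if removal differs by arm and is related to seizure risk. The figures for unequal removal rest on assumed rates and risk multiples. They show that the effect could range from none to material, and neither size nor direction follows from the document. It would be too strong to say that the randomised comparison is biased or destroyed.
- **Power.** If the 4% applies wholly on study, equally in both arms and without replacement, the cost is about one percentage point (0.900 to 0.888).
- **PHQ-9 outcome.** Truncation follows directly from Section 2.5 as written: patients who reach the threshold or endorse item 9 contribute no later scores. Their number is unknown. The 4% (32 of 804) is an upper reading for the threshold, because patients at or above it at entry are never randomised (3.3).

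**What to change.** Amend Sections 2.5, 3.4 and 4.5 so that they separate stopping study drug from leaving the study.

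- For PHQ-9, item 9, cancelled surgery, medical need and methotrexate, state that follow-up for seizure, survival and questionnaires continues to 12 months, whatever is decided about treatment. Only a patient who refuses further data collection leaves.
- In Section 7.3, state that all randomised patients are analysed in the arm allocated, including non-operated and prolonged-QT patients.
- In Section 3.4, state that further patients are additional recruits and do not substitute for anyone in the intention-to-treat set. Delete the words that tie them to the number for analysis.
- Sections 2.5, 3.3 and 3.4 describe severe depression and suicidal ideation differently (a PHQ-9 score, any non-zero item 9, active ideation, ideation on interview) and attach different consequences. The clinicians must reconcile them. Which rule should stop the drug is not a matter for this point.

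The cost is a protocol wording change and a note to sites. The visits concerned are already in the schedule in Section 4.3. The patient information should be checked so that it describes continued follow-up in the same way.

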2.6. Cognitive/capacity monitoring

Limited cognitive data that will be gathered for the study, at pre surgery (baseline) and 3 monthly visits –

- Semantic Verbal Fluency Test (SVFT) a test of Executive Function (taking approximately 1 minute)
- Anterograde Memory test Recall of a 7 item address after three attempts (taking approximately 2 minutes)
- Documentation on whether the treating clinician considers that the patient has or has not got on-going capacity.

If the clinician considers the patient has lost capacity. We would intend that if the patient has previously agreed that we can gather data in the event they suffer from cognitive decline then data collection would continue (Carer forms and record of first seizure, date, type and severity as determined by the treating clinician / Proxy)

The clinician will stop the study medication if they feel it is no longer safe for the patient to swallow tablets and the date of that decision will be recorded. Should a treatment break be required, e.g. in the event that it is deemed unsafe for the patient to swallow tablets, then standard of care treatment should be followed. This will not form part of the protocol. The clinician should consult with the patient carers and take note of any signs of objection or distress from the participant.

